**Research significance:**

**Background:**

Laparoscopic surgery for gastric reduction is frequently associated with high levels of postoperative pain. Postoperative pain is very often treated with opioids. However large doses of opioids can result in respiratory depression with hypoxemia especially in high risk patients with obstructive sleep apnea. Since a large group of patients undergoing surgery for gastric reduction surgery also have obstructive sleep apnea, it is expected that these patients are also at high risk for postoperative respiratory depression and hypoxemia.

Intraoperative ketamine has been used as an effective multimodal agent to reduce postoperative pain. However, ketamine alone has not been examined to improve postoperative pain outcomes in patients undergoing gastric reduction surgery. More importantly, it is unknown if the use of intraoperative ketamine can lead to better overall quality of recovery in the same patient population. In addition, ketamine has been shown to improve ventilation but it remains to be determined if the intraoperative use of ketamine will result in decreased postoperative opioid use and hence less complications such as hypoxic episodes within the first 24 hours after surgery.

The main objective of the current investigation is to examine the effect of intraoperative ketamine on postoperative quality of recovery after gastric reduction

surgery. We hypothesize that subjects receiving ketamine will have a greater global quality of recovery score than the ones receiving saline (placebo group). We also seek to determine if intraoperative ketamine would decrease the incidence of postoperative opioid requirements in the same patient population.

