#### **Methods:**

- 1. Primary outcome:** QoR-40 at 24 hours
- 2. Size of study groups(s):**  
It would be required to have 36 patients per group in order to achieve 80% power to detect a 10 point difference on the QoR-40 instrument with an estimated standard deviation of 15. To compensate for drop-outs or loss to follow-up, 80 patients will be recruited and randomized.
- 3. Secondary outcomes:**  
Postoperative opioid consumption  
Postoperative pain scores  
Length of hospital stay (Hours)
- 4. Patient entry, exclusion and dropout criteria:**  
**Entry:** Age 18-64, surgery: laparoscopic gastric reduction (gastric sleeve or gastric bypass), ASA I, II, III; BMI >35kg/m^2, Fluent in English  
**Exclusion:** History of allergy to protocol medications, History of chronic opioid use, pregnant patients.
- 5. Drop out:** Conversion to an open surgical route, patient or surgeon request.
- 6. Protocol specific methods:** Patients will be recruited on the day of surgery. Informed consent will be signed. Participant will complete the preoperative QoR-40 questionnaire (appendix 1) along with the Stop-BANG questionnaire (appendix 2). All medication except for propofol will be dosed based on the adjusted body weight (ABW=Ideal body weight (IBW) + [0.4 X (actual body weight –IBW)] Patients will be randomized using a computer generated table of random number to 2 groups: Group K (ketamine) will receive 0.5mg /kg of ketamine bolus followed by an infusion of 0.5 mg/kg/hour of ketamine throughout the intraoperative period. Group P (placebo) will receive the same amount of saline. The investigators will be blinded to study drug. The medication will be prepared by the hospital pharmacy and is not involved with the case or data collection.  
Subjects will be premedicated with midazolam (0.02-0.04 mg/kg IV preoperatively. Routine ASA monitors will be applied. Anesthesia will be induced with remifentanyl infusion started at 0.1 mcg/kg/minute titrated to keep blood pressure within 20% of the baseline and propofol 1.5 -2.5 mg/kg. Tracheal intubation will be facilitated with succinylcholine (1-2 mg /kg). Anesthesia will

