be maintained with sevoflurane titrated to a bispectral index (BIS) between 40-60, remifentanyl infusion started at 0.1mcg/kg/min titrated to keep blood pressure within 20 % of baseline values, and neuromuscular blockade will be maintained with rocuronium that will be administered at the discretion of the anesthesiologist. Upon termination of the surgery, residual neuromuscular blockade will be antagonized with a combination of neostigmine 0.05mg/kg (to a maximum dose of 5mg) and glycopyrrolate 0.01 mg/kg . Remifentanyl will be discontinued at the time of the removal of the laparoscope from the abdomen and hydromorphone 10 mcg/kg IV will be administered. Ondansetron 4 mg IV and dexamethasone 4 mg IV will be administered to prevent postoperative nausea and vomiting. Study drug will be discontinued at the end of the surgical procedure as the dressings are being placed. Normothermia will be maintained intraoperatively using a forced air warming blanket (Bairhugger, Arizant healthcare INC, Eden Prairie, MN). Subjects will receive IV Hydromorphone in divided doses as needed to achieve a verbal rating score for pain <4 out of 10 starting in the operating room following extubation and in PACU. Metoclopramide (10 mg IV) will be used as rescue antiemetic. Patient-controlled analgesia, programmed to deliver 0.2 mg of hydromorphone every 10 minutes, will be instituted before the patient is discharged from the PACU. Before PACU discharge, the LSD ARCI questionnaire (appendix 3) will be completed by the patient to assess for other untoward effects of ketamine. Ketorolac 30 mg every 6 hours for 24 hours will be started when admitted to patient room. SpO2 will be monitored continuously for 24 hours after discharge from PACU. At 24 hours after surgery patients will complete the QoR-40 (appendix 1) instrument.

**Risks/Benefits:** Participants may not have any direct benefit from taking part in this study. Taking part in this study may help us determine whether the study drug increases 24 hour quality of recovery and decreases opioid requirements within 24 hours of the surgery.

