**Normal Saline (placebo):**

Hypernatremia

These side effects are uncommon with the lower dose range used in this study.

There is a risk of loss of confidentiality even though there are strict measures in place to prevent occurrence. Answering some of the questionnaires or surveys may make subject feel uncomfortable. The subject may skip to the next question if the question upsets them. There is a very slight risk of skin irritation from the pulse oximeter (Konica Minolta).

**Confidentiality:** Subjects' identity will be guarded by assigning a numerical code which is only known by the principal investigator and research coordinator. Data will be stored in department computer which is password protected. Each study subject will be assigned a study code number. The code will be used to link study data to patient identification (name) in a separate database. Subject data will be stored on secure computers at Northwestern University. Data access will be password protected and only available to study investigators. The data forms will be de identified after the chart review prior to analysis. 7 years post manuscript completion the data both electronic and paper will be destroyed using current departmental approved methods of destruction.

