**Appendix 2 (STOP-Bang Questionnaire)**

**STOP-Bang Questionnaire**

	YES	NO
Snoring: Do you snore loudly (loud enough to be heard through closed doors)?		
Tired: Do you often feel tired, fatigued, or sleepy during daytime?		
Observed: Has anyone observed you stop breathing during your sleep?		
Blood pressure: Do you have or are you being treated for high blood pressure?		
BMI: more than 35 kg m  ?		
Age: over 50 year old?		
Neck circumference: >40 cm?		
Gender: Male?		
Total Score		
PACU Desaturation		

High risk of OSA: Yes to ≥3 questions.

Low risk of OSA: Yes to <3 questions.

Chung F, et al: BJA 2012; 108: 768-75

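### Does 24 hours of SpO2 monitoring after PACU put a floor under length of hospital stay that calls for a change to the plan?

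*Combined protocol and SAP*

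**What the plan says.** Methods, item 6, describes care after the patient leaves PACU: "SpO2 will be monitored continuously for 24 hours after discharge from PACU". Patient-controlled hydromorphone is already running by then, and a ketorolac course begins on the ward: "Ketorolac 30 mg every 6 hours for 24 hours will be started when admitted to patient room".

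Methods, item 3, names three secondary outcomes: opioid use, pain scores and "Length of hospital stay (Hours". No clock start, clock end or discharge criteria are given for the last. None of the three uses SpO2, and no desaturation threshold or summary is defined.

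Three other places touch on oxygenation. The Background raises as an open question whether ketamine leads to "decreased postoperative opioid use and hence less complications such as hypoxic episodes within the first 24 hours after surgery". The risks text mentions the oximeter: "There is a very slight risk of skin irritation from the pulse oximeter (Konica Minolta". Appendix 2, the STOP-Bang form, carries an undefined line, "PACU Desaturation", although item 6 has that form completed before surgery: "Participant will complete the preoperative QoR-40 questionnaire (appendix 1) along with the Stop-BANG questionnaire (appendix 2".

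**The concern.** A procedure that keeps every participant in hospital for a fixed time limits how short a stay can be. Two patients ready to leave 16 and 22 hours after PACU would both be recorded at 24 hours or later, and the difference between them would vanish. A real shortening of stay with ketamine would be pulled towards zero, and a null result could be read as no benefit.

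The point looks sharper because the monitoring feeds no listed outcome, so it might seem to cost the trial information and return none. The time windows also differ: the Background speaks of the first 24 hours after surgery, whereas monitoring starts only at PACU discharge.

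**Working it through.** **The plan's own figure.** The only sample-size calculation is for the QoR-40. With a difference of 10, SD 15 and 80% power (item 2), and assuming two-sided alpha of 0.05, which is not stated: n = 2 × (1.960 + 0.842)² × 15² / 10² = 35.3, so 36 per group, as the plan says. With 80 randomized there are 40 per arm. Nothing is sized on length of stay.

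**Is there a floor?** A minimum of PACU time plus 24 hours needs two things: monitoring takes place in hospital, and discharge waits for it to end. The neighbouring text (patient room, patient-controlled analgesia) makes the first likely. The second is not written. The floor is therefore a reasonable inference and not a stated rule.

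**How much would a floor cost?** Let T be the time from PACU discharge until a patient would otherwise leave. The following are assumptions: T is lognormal with placebo median m, ketamine median m − 4 hours and log-SD s. With floor c, the recorded time is max(T, c), with mean

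E = c × Φ((ln c − ln m)/s) + m × exp(s²/2) × Φ((ln m + s² − ln c)/s).

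Example with m = 24, s = 0.35, c = 24:
- Placebo: 24 × 0.500 + 25.52 × 0.637 = 28.25 h.
- Ketamine (median 20): 24 × 0.699 + 21.26 × 0.432 = 25.96 h.
- Recorded difference 2.29 h; difference without a floor 25.52 − 21.26 = 4.25 h; retained 2.29/4.25 = 0.54.

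| Placebo median after PACU | Placebo patients ready before 24 h | Mean difference retained, s = 0.25 / 0.35 / 0.50 | Rank-sum power, 40 per arm, s = 0.35: no floor, then floor |
|---|---|---|---|
| 24 h | 50% | 0.46 / 0.54 / 0.63 | 60%, 51% |
| 30 h | 19–33% | 0.80 / 0.78 / 0.79 | 43%, 39% |
| 36 h | 5–21% | 0.95 / 0.91 / 0.88 | 30%, 31% |
| 48 h | 0–8% | 1.00 / 0.99 / 0.96 | 18%, 18% |

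The power figures are simulated (3,000 runs); the last two pairs differ only by simulation error.

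**How much of that belongs to the SpO2 rule?** The table compares a 24-hour floor with none. Ketorolac would hold patients too. If doses fall at 0, 6, 12 and 18 hours and discharge follows the last, the floor without SpO2 is already about 18 hours, counting room admission as PACU discharge. With c = 18 and m = 24 the formula gives 0.85 / 0.82 / 0.81 retained, so part of the loss is there before SpO2 is considered. If the ketorolac course is taken to fill its 24 hours, SpO2 adds almost nothing.

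**The windows.** With a PACU stay of p hours, monitoring runs from p to p + 24 hours after surgery and overlaps the Background's window for 24 − p hours. For an assumed p of 1 to 3 hours that is 21 to 23 hours. Since hypoxaemia is not an outcome, no planned analysis depends on the mismatch.

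**The case for a change.** The strongest case for acting is that an outcome measured in hours ought to be defined, that the natural reading of item 6 is inpatient monitoring, and that one recorded time per patient (when discharge criteria are first met) would separate recovery from protocol. If ketorolac also holds patients in hospital, that strengthens the view that recorded stay partly reflects the protocol.

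Some of this stands. Length of stay is undefined, the in-hospital reading is the likelier one, and if most patients would otherwise leave about a day after PACU, the attenuation is real.

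The remedy is less secure. Time to readiness is a different endpoint from actual stay. It needs staff to check patients repeatedly against criteria that the documents do not contain, and if those criteria require analgesia or monitoring to be finished, the same floor returns. Singling out SpO2 also attributes to one element what belongs to a roughly 24-hour ward pathway.

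Nor is the monitoring without a reason. The Background describes opioid-related respiratory depression and hypoxaemia in a population with frequent sleep apnoea, which is a plain safety rationale. Safety monitoring need not be an outcome. The Appendix 2 line is a loose form entry; it sits below the total score, and nothing prevents staff from filling it in later.

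**Conclusion.** No change to the plan follows. The floor is inferred, it is shared with the ketorolac course, and the rule is the same in both arms, so it could shrink a difference but not create one. It bears on a single secondary outcome for which the trial is not powered: even with no floor, power for the assumed 4-hour effect is only about 18 to 60%, so a null result on stay would say little in any case.

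The loss is material only if many patients would be ready within about 24 to 30 hours of leaving PACU, and nothing in the documents indicates that. At a 36-hour median it is 5 to 12% of the mean difference, with no visible change in power. These sizes rest on assumed lognormal ready times, log-SDs of 0.25 to 0.50 and a 4-hour benefit.

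What remains is missing detail of a kind analysts ordinarily settle: count hours from one common start to recorded discharge in both arms, treat SpO2 as safety monitoring, and note when reading the result that protocol care may have limited early discharge. The primary QoR-40 comparison, "Postoperative opioid consumption" and pain scores are unaffected.

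### Does timing SpO2 monitoring from PACU discharge, with no hypoxaemia outcome listed, leave a question of the trial unanswered?

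*Combined protocol and SAP*

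**What the plan says.** The Background explains that patients having this surgery often have sleep apnoea and are at risk of opioid-related respiratory depression. It then says "it remains to be determined if the intraoperative use of ketamine will result in decreased postoperative opioid use" and, through that, "less complications such as hypoxic episodes within the first 24 hours after surgery".

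Under Methods, item 6, the monitoring sentence reads "SpO2 will be monitored continuously for 24 hours after discharge from PACU". The same item has IV hydromorphone titrated to pain "starting in the operating room following extubation and in PACU", and it times the primary endpoint from surgery: "At 24 hours after surgery patients will complete the QoR-40".

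Methods, items 1 and 3, list the outcomes: QoR-40 as primary; opioid consumption, pain scores and length of hospital stay as secondary. No threshold, definition or analysis of hypoxaemia appears anywhere.

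Two other places touch on oximetry. The risk section says "There is a very slight risk of skin irritation from the pulse oximeter". The STOP-Bang form in Appendix 2 carries a row labelled "PACU Desaturation", with no definition.

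**The concern.** Read together, these places suggest a question that was raised, a signal collected to answer it, and no outcome to link the two. The clock also looks wrong. Starting at PACU discharge leaves out the period when hydromorphone is being titrated soon after anaesthesia, and it runs past the 24 hours named in the Background. PACU discharge comes after randomisation, so treatment could shift it, and the two arms might then be observed over different stretches of the postoperative course.

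If a hypoxaemia result were reported later, its threshold and window would have been chosen after the data existed. PACU readings that were never stored could not be recovered.

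**Working it through.** **Step 1. Aims against outcomes.** Where the protocol states what it sets out to learn, it names the following:

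- Research Aims: one question and one hypothesis, both on quality of recovery.
- Background, closing paragraph: the main objective is quality of recovery; the one further aim is opioid requirement.
- Risks/Benefits: the same two, quality of recovery at 24 hours and opioid requirement within 24 hours.

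Methods, item 1, serves the first aim (QoR-40) and item 3 serves the second (opioid consumption). Hypoxic episodes appear in none of these statements of aim. They occur in the rationale, as an example of what might follow from lower opioid use. No stated aim lacks an outcome.

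**Step 2. Size of the window mismatch.** The documents do not give the PACU stay, so let H be an assumed number of hours from end of surgery to PACU discharge (PACU arrival taken as end of surgery). The monitoring then runs from hour H to hour 24 + H, and the uncovered share of the first 24 hours is H/24.

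| Assumed H | Monitoring runs | Uncovered | Covered |
|---|---|---|---|
| 1 h | hours 1 to 25 | 1/24 = 4.2% | 95.8% |
| 2 h | hours 2 to 26 | 2/24 = 8.3% | 91.7% |
| 3 h | hours 3 to 27 | 3/24 = 12.5% | 87.5% |

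These are shares of time, not of events. If desaturation clusters early, the share of events missed would be larger; the documents give no rates from which to judge. The excess beyond 24 hours does no harm, since time-stamped readings can be cut there.

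**Step 3. What an added outcome could show.** The plan's own size comes first. With a difference of 10, SD 15 and 80% power (Methods, item 2), and assuming two-sided 5% and equal allocation, neither of which is stated:

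n per group = 2 × (1.960 + 0.842)² × 15² / 10² = 35.3, rounded up to 36. This matches the plan. Allowing for 10% loss, 72 / 0.90 = 80, which also matches.

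Now take any desaturation as a yes/no outcome with 36 per group. The placebo rates p1 are assumptions, and p2 = p1/2:

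- 95% CI half-width = 1.96 × √[(p1(1 − p1) + p2(1 − p2)) / 36]
- Power = Φ{[(p1 − p2) − 1.96 × √(2p̄(1 − p̄)/36)] / √[(p1(1 − p1) + p2(1 − p2)) / 36]}, where p̄ is the mean of p1 and p2

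| p1 vs p2 | Half-width | Power |
|---|---|---|
| 10% vs 5% | 12.1 points | 12.3% |
| 30% vs 15% | 19.0 points | 32.9% |
| 50% vs 25% | 21.6 points | 59.4% |

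Worked for the middle row: √[(0.21 + 0.1275)/36] = 0.0968, times 1.96 = 0.190; √(2 × 0.225 × 0.775/36) = 0.0984; (0.150 − 0.193)/0.0968 = −0.44, and Φ(−0.44) is about 0.33.

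Even a halving of the rate would leave, in the first two rows, an interval wider on each side than the difference itself.

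**The case for a change.** The best argument for a change is that the oximetry looks like a research procedure. A named oximeter is listed among the study's risks, sleep apnoea is screened for, and the STOP-Bang form, which patients complete before surgery, has a row that can only be filled in afterwards. If the sponsor means to report hypoxaemia, then the threshold, the measure and the time origin should be fixed before unblinding. Low precision makes that more important, because a chance finding is easiest to produce when the definition is still open. Starting at PACU arrival would also bring the window closer to the end of surgery and include the hydromorphone titration.

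Much of this stands, but only on that condition. Nothing in the documents plans such a report. The monitoring sentence sits among the ward-care steps, in patients the Background calls high risk, so monitoring for safety is an equally plausible reading; the documents do not settle which is meant. The point about the post-randomisation start is sound in principle, but neither the direction nor the size of any difference in PACU time can be derived from the documents, and every patient has the same planned 24 hours of monitoring. That the oximetry and the questionnaire run on different clocks is not an error in itself. Earlier data capture would also depend on having the study oximeter and staff in the PACU, on which the documents are silent.

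**Conclusion.** No change to the plan is needed. Followed as written, it gives no wrong result and no wrong conclusion: the primary outcome and all three secondary outcomes are untouched by where the SpO2 clock starts. The gap is between a remark in the rationale and a monitoring step, and it amounts to 4.2% to 12.5% of the first 24 hours at an assumed PACU stay of 1 to 3 hours. A new hypoxaemia outcome would be one the trial is not sized for, with power of 12% to 59% under the assumed rates and halving shown above.

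Two things remain true. The protocol does not say whether SpO2 is kept for safety or for research, and the PACU desaturation row is undefined. A sentence on each would help a reader but is optional. The conclusion rests on no hypoxaemia comparison being intended. Any that is reported should be labelled exploratory, with its threshold, window and time origin stated.

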#### **Side effects of ketamine**

The common side effects of the study drug ketamine include:

#### **Most Frequent:**

Delirium  
Hallucinations  
Mood changes  
Nightmares  
Tachyarrhythmia  
Tonic- Clonic Epilepsy  
Vocalization

#### **Less Frequent:**

Bradycardia  
Hypotension

Respiratory Depression  
Vomiting

**Rare:**

Anaphylaxis  
Anorexia  
Conduction disorder of the heart  
Diplopia  
Injection site  
Laryngismus  
Nausea  
Nystagmus  
Obstructive pulmonary disease  
Skin inflammation  
Skin rash

**Normal Saline (placebo):**

Hypernatremia

These side effects are uncommon with the lower dose range used in this study.

There is a risk of loss of confidentiality even though there are strict measures in place to prevent occurrence. Answering some of the questionnaires or surveys may make subject feel uncomfortable. The subject may skip to the next question if the question upsets them. There is a very slight risk of skin irritation from the pulse oximeter (Konica Minolta).

**Confidentiality:** Subjects' identity will be guarded by assigning a numerical code which is only known by the principal investigator and research coordinator. Data will be stored in department computer which is password protected. Each study subject will be assigned a study code number. The code will be used to link study data to patient identification (name) in a separate database. Subject data will be stored on secure computers at Northwestern University. Data access will be password protected and only available to study investigators. The data forms will be de identified after the chart review prior to analysis. 7 years post manuscript completion the data both electronic and paper will be destroyed using current departmental approved methods of destruction.

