**Have you had any of the following in the last 24 hours? (please circle one)**

	None of the time	Some of the time	Usually	Most of the time	All of the time
COMFORT					
Nausea	5	4	3	2	1
Vomiting	5	4	3	2	1
Retching	5	4	3	2	1
Feeling restless	5	4	3	2	1
Shaking / twitching	5	4	3	2	1
Shivering	5	4	3	2	1
Feeling cold	5	4	3	2	1
Feeling dizzy	5	4	3	2	1
EMOTIONS					
Had bad dreams	5	4	3	2	1
Feeling anxious	5	4	3	2	1
Feeling angry	5	4	3	2	1
Feeling depressed	5	4	3	2	1
Feeling alone	5	4	3	2	1
Had difficulty falling asleep	5	4	3	2	1
PATIENT SUPPORT					
Feeling Confused	5	4	3	2	1

	None of the time	Some of the time	Usually	Most of the time	All of the time
PAIN					
Moderate pain	5	4	3	2	1
Severe pain	5	4	3	2	1
Headache	5	4	3	2	1
Muscle pains	5	4	3	2	1
Backache	5	4	3	2	1
Sore throat	5	4	3	2	1
Sore mouth	5	4	3	2	1

Please check that all questions have been answered.

Thank you for your assistance.

Date: \_\_\_ / \_\_\_ / \_\_\_

Time: \_\_\_\_\_ AM / PM

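### Does the permission to skip upsetting questions undermine the 40-item QoR-40 primary outcome?

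*Combined protocol and SAP*

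**What the plan says.** Methods, items 1 and 2, name the "QoR-40 at 24 hours" as primary outcome and size the trial on it, with 36 patients per arm for 80% power. The target is a gap of 10 points between arms, and the sample size was worked out "with an estimated standard deviation of 15". Eighty patients are randomised to cover drop-out and loss to follow-up.

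The Risks/Benefits text, in the paragraph printed below the saline side effects, warns that some questionnaires may cause discomfort and adds: "The subject may skip to the next question if the question upsets them". This is general wording. It covers the STOP-Bang and LSD-ARCI forms as well as the QoR-40.

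The QoR-40 form in Appendix 1 ends with the opposite request: "Please check that all questions have been answered". Its items include "Had bad dreams" and others on anxiety, anger, depression, loneliness and confusion. The side-effect section puts nightmares, mood changes, hallucinations and delirium among ketamine's most frequent effects. The text after the side-effect lists then calls these effects uncommon at the dose range used here.

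No section states how the total is formed, what happens to a blank item, or how many items must be answered.

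**The concern.** A trial powered on a points total needs a total for every patient, yet the protocol permits blanks in the form that produces it. Two careless treatments of a blank would do harm. A plain sum counts it as 0, below the worst valid answer of 1. A complete-case analysis discards the whole patient, and the margin for losses is only 8 patients.

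The permission is also tied to being upset, so blanks need not be random. Patients with bad dreams or low mood might skip the items asking about them, and ketamine might make such patients more common in one arm. Zero-scoring would then penalise that arm, while exclusion could hide its poor scores. At stake would be bias in the primary comparison, loss of power, and freedom to choose the handling after seeing the data.

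**Working it through.** **The plan's own figure.** Inputs from Methods, item 2: difference 10, SD 15, power 80%. Alpha is not stated; two-sided 0.05 is assumed.

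n per group = 2 × (1.960 + 0.842)² × 15² / 10² = 35.3, rounded up to 36.

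This matches the protocol. The t-test version gives 36.3, and a one-sided 0.05 test would give 28, so two-sided 0.05 is the evident basis. The allowance is 1 − 72/80 = 10%. Power by t-test is 83.8% at 40 per arm and 79.7% at 36.

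**The form.** Appendix 1 has 4+3+5+6 = 18 positive items and 8+6+1+7 = 22 negative items, 40 in all. By dimension: comfort 12, emotions 9, physical independence 5, patient support 7, pain 7. A complete form scores 40 to 200.

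**If blanks scored zero.** One patient with two blanks loses 2 to 10 points. That is an individual score. The design difference is between arm means, and to move an arm's mean by 10 every patient in it would have to skip two items worth 5 each.

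At arm level, loss = (number of items) × (excess skip rate) × (score the item would have had). All skip rates here are assumptions.

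| Items | Excess per item | Score forgone | Loss | Effect left | Power, 36/arm |
|---|---|---|---|---|---|
| 6 | 5% | 1 | 0.3 | 9.7 | 77% |
| 6 | 10% | 2 | 1.2 | 8.8 | 69% |
| 7 | 5% | 2.5 | 0.9 | 9.1 | 72% |
| 7 | 10% | 4 | 2.8 | 7.2 | 52% |

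The first two rows fit the proposed mechanism best. A patient who skips an item because the symptom is present would have scored near 1 or 2 on it. The last two rows add the item on falling asleep and give skippers middling to good scores, which the mechanism does not support.

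**If any blank removed the patient.** With independent skipping at rate p on all 40 items, P(incomplete) = 1 − (1 − p)^40. But if upset is the cause, skips cluster in a few items and a few patients. The same p can be recomputed with only 7 items ever skipped, 1 − (1 − p)^7, or with the same mean number of skips but four per skipper, 40p/4:

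| p | All 40, independent | Only 7 items | Four per skipper |
|---|---|---|---|
| 0.25% | 9.5% | 1.7% | 2.5% |
| 0.5% | 18.2% | 3.4% | 5% |
| 1% | 33.1% | 6.8% | 10% |

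The alarming column contradicts the reason given for expecting skips. If 10% were lost to skipping on top of 10% ordinary drop-out, 40 × 0.9 × 0.9 = 32.4 per arm would remain, with power 75%.

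**If blanks were prorated within a dimension.** Suppose a patient averages 4 on the answered items and would have scored 2 on the blank one. The total is overstated by 2 points per blank. With six items and a 5 to 10% excess, the arm gains 6 × 0.05 × 2 = 0.6 to 6 × 0.10 × 2 = 1.2 points. Under the same assumed mechanism, the sensible rule leaves an error similar in size to zero-scoring at true scores of 1 to 2, in the other direction.

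**The case for a change.** The strongest case is that the protocol itself authorises blanks in its primary endpoint, for a reason linked to the patient's state, and does not say how to score them. Zero-scoring and exclusion err in different directions, so an unwritten rule leaves room for choice once results are visible. The 10% allowance is assigned to drop-outs and loss to follow-up, not to blank items. Writing a rule would take a few lines.

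Much of this stands: the rule is missing, blanks related to distress are conceivable, and the request to check every answer sits awkwardly beside the permission to skip. Three parts do not carry over.

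- Lowering the total and losing the patient are not the only outcomes. Proration and imputation do neither, and they are the usual treatment of a few blanks in a multi-item scale.
- That ketamine-related items will be skipped most is an inference. The documents hold no skip data, and they describe the relevant effects as uncommon at this dose range.
- A written rule of proration with at least half of a dimension answered would not close the question. It must still say what happens below half, and it replaces distress items with the average of the others. Informative blanks remain a limitation under any such rule, to be judged from the number of blanks in each arm.

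**Conclusion.** No change follows. This is a scoring detail left unwritten in a short protocol that also names no primary test or analysis set, and analysts can fill it sensibly. No stated rule gives a wrong result, and the two damaging treatments are not in the plan.

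The permission to skip is a reasonable courtesy to participants, and the form's closing request limits its use. The two can be read together: answer everything unless a question is upsetting.

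The size is conditional throughout. Under zero-scoring, with six sensitive items each skipped 5 to 10 percentage points more often in the ketamine arm and true scores of 1 to 2, the loss is 0.3 to 1.2 points and power is 77% to 69% instead of 80%. These figures assume a true 10-point effect, SD 15, two-sided 0.05 and 36 per arm. With few or balanced blanks and ordinary proration, the effect on the comparison would be negligible. Skipping that was frequent and clearly unequal between arms would change this view, but nothing in the documents points to it.
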